#### PK Sampling

Blood samples will be used to establish population pharmacokinetics. Scavenged blood samples of 0.05 mL of blood will be collected from all clinical blood draws throughout the infant’s hospitalization and sent to the University of Iowa for population pharmacokinetics using meso-scale discovery assay to detect Epo levels. Since a baseline sample is also required for immunogenicity testing we will collect an extra 0.3 mL of blood with the “pre-drug” blood work drawn in the NICU. Study participants will have the option of opting in for this additional blood draw. This will ensure that there is enough blood for potential immunogenicity testing and pK analysis. Every effort will be made to obtain this sample with a blood draw that is needed for clinical purposes (such as a glucose check). All other pk samples will be off of scavenged blood. Parents will be given the option to opt into this part of the study on the consent form.

Parents of participants will be contacted by phone call at 4 months of age which will include developmental screening via a modified Ages and Stages questionnaire (attached), number of hospitalizations, seizures, need for assisted respiratory support, failure to thrive, medication use, use of early intervention services, hearing impairment, any concern with vision.

Participants will have neurodevelopmental testing (Bayley III and Gross Motor Function Assessment) performed at 8-12 months of age. We will also conduct a brief medical exam including weight, length, head circumference, blood pressure, and heart rate.

In addition, we may contact the child’s primary care provider and ask for the baby’s most recent medical history and the result of the most recent hematocrit.

Data will be kept for analysis for up to 10 years.

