### **Safety**

For the purpose of this study, an **adverse event** (AE) will be defined as any adverse change from the patient's baseline condition that occurred following the administration of the study drug through the end of the study period. Safety will be evaluated during the first 7 days of life or until hospital discharge (whichever comes first) by documenting potential adverse events such as (but not limited to) alterations in blood pressure, secondary infections, neutropenia, thrombotic/vascular events, hematologic events (platelets, Hct level, polycythemia), and hepatic/renal function that are outside of normal range for the study population.

We will assess for the rare complication (1 in 10,000 in adults with renal failure) of pure red blood cell aplasia. The vast majority of babies admitted to the NICU have a CBC with diff drawn on admission. If there is at least 0.5mL of blood remaining (scavenged blood) after analysis, we will collect that blood and use as our baseline sample. Similarly, most babies admitted to the NICU have electrolytes or bilirubin levels drawn at 24-72 hours of age, if there is at least 0.5mL of blood remaining (scavenged blood) after analysis, we will collect that blood and use as our second sample. If the baby remains in the NICU for 2 weeks (uncommon) and has a blood test done for clinical reasons, we will attempt to keep 0.5mL (scavenged blood) to assess for pure blood cell aplasia. Additionally, a letter (attached) will be given to the PCP stating that the patient is enrolled in a research study. If there are concerns for anemia and the PCP orders a CBC within the first year of life we will ask for 0.5mL of blood (scavenged blood). We will ask the lab to hold "scavenged" blood and store for up to 6 months beyond enrollment of the last patient.

We will also ask for the medical records from the child's primary care provider and their most recent hematocrit/hemoglobin.

**Long Term Safety** will involve phone calls at 4 months of age which will include developmental screening via Ages and Stages questionnaire, hospitalizations, seizures, need for assisted respiratory support, failure to thrive, medication use, use of early intervention services, hearing impairment, any concern with vision. In addition we will contact the child's primary care provider and ask for the child's medical records and most recent hematocrit/hemoglobin to assess for safety.

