**Serious adverse events** (SAE) will be defined as any event that results in: death, a life threatening event (major venous thrombosis, stroke, and/or severe hypertension), persistent or significant disability/ incapacity, and/or prolongs inpatient hospitalization.

SAEs will be reported until 30 days following final cessation of therapy or until hospital discharge, whichever comes first.

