### **6. Provisions to Monitor the Data to Ensure the Safety of Subjects**

The data and safety monitoring board (DSMB) is composed of members qualified by training and experience to monitor the progress of the investigation:

- 1) [name] Professor of Neurology, University of New Mexico. [name] will be the DSMB Chair for this project.
- 2) [name]. Professor of Pediatrics, University of New Mexico. [name] has led and conducted multiple multicenter clinical studies .
- 3) [name]. Division of Neuroscience, Department of Pediatrics, University of New Mexico
- 4) [name]. Professor of Pediatrics, Nationwide Children's Hospital, Columbus, Ohio.

Monitoring plan will include:

- 1) The DSMB will review the study data for non-compliance and participant safety (adverse events, unanticipated problems, etc.) after the first 20 patients have been enrolled and every 6 months until study completion

- 2) The DSMB will report their findings to the sponsor-investigator after each meeting
- 3) The sponsor-investigator will report DSMB findings to all participating clinical investigators after each meeting. Each participating investigator will submit the DSMB review to their IRB with corresponding documentation of the submission sent to [name]
- 4) All SAEs will be reported to [name] within 24 hours of the site learning of the event. Each site PI will be responsible for reporting the serious or unexpected adverse events to their local IRB in accordance with the local IRB policies. [name] will be responsible for notifying the DSMB chair within 24 hours of receiving the report and notifying the FDA in an IND safety report in accordance with FDA regulations. The DSMB will determine if the adverse event changes the risk to study subjects. If the information changes the known risk to subjects, the DSMB report of this event will be released to all participating investigators by [name].
- 5) Criteria for Withholding Study Drug: Neutropenia (ANC <500/ $\mu$ L), hematocrit of >65%, stroke, symptomatic clot, or hypertension (blood pressure 2 SD greater than the mean for age).

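### A readmission is not in itself an SAE and SAE reporting closes at discharge, so the hospitalisations collected at follow-up cannot enter the expedited safety route

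*Combined protocol and SAP*

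**What the plan says.** All references are to the combined protocol and SAP.

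- **SAE definition (Section 3, Safety).** An event is serious if it results in death, "a life threatening event (major venous thrombosis, stroke, and/or severe hypertension"), or "persistent or significant disability/ incapacity, and/or prolongs inpatient hospitalization". Neither a new admission nor a general criterion for other medically important events is listed.
- **SAE window (the sentence after the definition).** "SAEs will be reported until 30 days following final cessation of therapy or until hospital discharge, whichever comes first".
- **Adverse events (same part).** AEs are defined as changes "following the administration of the study drug through the end of the study period", but the evaluation period is shorter: "Safety will be evaluated during the first 7 days of life or until hospital discharge (whichever comes first"). The list of AEs is expressly open: "documenting potential adverse events such as (but not limited to) alterations in blood pressure".
- **Follow-up.** The 4-month telephone call asks for "number of hospitalizations, seizures, need for assisted respiratory support" and other items (follow-up text under PK Sampling). The Long Term Safety paragraph includes hospitalisations in that call. The schedule of evaluations repeats the survey at 8-12 months corrected age.
- **Reporting route (Section 6, item 4).** "All SAEs will be reported to" the sponsor-investigator within 24 hours. Notice to the DSMB chair and the IND safety report to the FDA follow from that report.

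**The concern.** The protocol regards later hospitalisations as safety information, since it asks about them under Long Term Safety. It also looks for one named late harm, pure red cell aplasia, through blood counts ordered by the primary care provider during the first year. Yet its SAE rules give a readmission no way into expedited review. An admission that starts after the birth stay prolongs nothing, so it meets no SAE criterion unless it also involves death, a listed diagnosis or lasting disability. Even then, the reporting window has already closed.

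There is a second, smaller problem inside the window. The three life-threatening diagnoses carry no wording to show that they are examples, whereas the AE list just before them does. A site could reasonably read them as the full list and not report a different life-threatening event as serious, unless it was fatal, disabling or prolonged the stay. Seven centres are named in the study timeline, and they may not all read the sentence alike.

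At stake is prompt notice of harm to the sponsor-investigator, the DSMB chair and the FDA, in a blinded IND trial in newborns.

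**Working it through.** The documents give no figure on this point, so the check sets the rules side by side and asks which events reach Section 6, item 4. An event must pass two tests: it meets the SAE definition, and it falls inside the SAE window.

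**Step 1: when the window closes.** Section 7 describes a single intervention, given before 24 hours of age, so therapy ends on the day of dosing. The window therefore closes at the earlier of about day 30 and hospital discharge, and never later than discharge. A readmission comes after discharge by definition, so it is always outside.

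**Step 2: which readmissions meet the definition.** Those involving death, a listed diagnosis or lasting disability do. A readmission for another reason, followed by recovery, does not.

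**Step 3: what each possible change achieves.**

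| Rules applied | Readmission with recovery, no listed diagnosis | Readmission with death, a listed diagnosis or lasting disability |
|---|---|---|
| As written | Fails definition and window: not routed | Meets definition, fails window: not routed |
| Definition widened only | Meets definition, fails window: not routed | Fails window: not routed |
| Window lengthened only | Fails definition: not routed | Routed |
| Both changed | Routed | Routed |

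The definition and the window are independent blocks. Widening the definition alone routes no readmission and would leave it at odds with the window sentence. Lengthening the window alone still leaves out the admissions in the first column.

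**Step 4: what other routes remain.** Section 6, item 1 has the DSMB review adverse events and unanticipated problems after the first 20 patients and then every 6 months. Item 4 also sends unexpected adverse events, serious or not, to the local IRB. Section 4 requires prompt reporting of unanticipated problems to IRBs. The Safety part asks for primary care records. None of these is limited to SAEs. It is unclear, however, whether a readmission is recorded as an AE at all, because AEs are defined to the end of the study but evaluated only to day 7 or discharge.

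**Step 5: size.** A count of affected events would need a readmission rate. The documents give none, so no number is offered.

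**The case against.** The strongest objection is that the window, not the definition, is what stops a readmission from being reported today. All eligible infants are managed in the NICU, so during the window prolongation is normally the only hospitalisation criterion that can apply. This stands in full, and it is why the definition and the window must be changed together.

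It can also be said that following later admissions through structured calls is a legitimate choice after one dose. Section 2 cites half-lives of 24 to 35 hours for darbepoetin in cooled infants, and many later admissions will be unrelated infant illnesses. That is fair as an argument about workload. It does not explain why a death or stroke after discharge, which the definition already calls serious, has no expedited route.

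Four stronger readings are tempting, and the documents do not support them:

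- *That a readmission is never a serious event.* Some readmissions meet the definition; they fail only on the window.
- *That hospitalisations reach the database only as a count.* The telephone text mentions a number, but the Long Term Safety paragraph and the schedule refer to hospitalisations generally, and primary care records are also requested. The survey form is not shown, so it cannot be said that date and reason are absent from it.
- *That the DSMB sees readmissions only as a tally every 6 months, or not at all.* The routes in Step 4 remain, and the FDA step is tied to FDA regulations. What is lost is the expedited notice.
- *That planned accrual measures the gap.* With 80 infants in 24 months, 80 / 24 = 3.33 per month, or 3.33 x 6 = 20 between 6-monthly reviews. That is enrolment under an even rate, not a number of missed events.

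The closed reading of the three diagnoses is likewise an inference. The contrast with the open AE list supports it, but an illustrative reading is possible.

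**Conclusion.** The point holds in this form. A new admission or readmission does not by itself make an event serious, and SAE reporting ends no later than discharge. As written, therefore, no post-discharge readmission enters the 24-hour, DSMB-chair and IND safety report route, although the plan collects hospitalisations at 4 and 8-12 months and classes them as long-term safety information. The loss is one of expedited notice. Periodic DSMB review, primary care records and IRB reporting remain, with some doubt about whether late admissions are captured as AEs. The number of events affected is unknown.

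The conclusion assumes that hospital discharge means the end of the birth stay, and that sites apply the definition and the window literally. It does not depend on whether the three diagnoses are a closed list; that ambiguity is a separate reason to clarify the sentence. This is a cheap improvement to safety reporting and does not affect the primary analysis.

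**What to change.** Make these changes in one amendment:

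1. In the SAE definition (Section 3, Safety), replace the prolongation criterion with: *requires inpatient hospitalization (including readmission) or prolongs it*. Put *for example* before the three life-threatening diagnoses.
2. Amend the SAE window sentence that follows, so that it is consistent with the Long Term Safety follow-up and the surveys at 4 and 8-12 months.
3. Have those surveys record the date and reason of each admission, if the forms do not already do so.
4. State that any admission meeting the revised definition goes through the SAE route in Section 6, item 4, starting when the site learns of it.

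The cost is a few sentences and up to two survey fields. The real downside is more SAE reports, many of them for unrelated infant illnesses, which the sponsor-investigator and the DSMB chair must triage.

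### SAE reporting stops at hospital discharge if that comes before 30 days after the dose; this is not reconciled with the rest of the safety plan, and serious events learned later have no stated handling

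*Combined protocol and SAP*

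**What the plan says.** The provisions sit in sections 3, 6 and 7.

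- **SAE period (section 3, Safety, serious adverse events):** "SAEs will be reported until 30 days following final cessation of therapy or until hospital discharge, whichever comes first". The SAE definition covers death, life-threatening events (major venous thrombosis, stroke, severe hypertension), lasting disability, and an event that "prolongs inpatient hospitalization".
- **AE definition (section 3, Safety):** an adverse change from baseline that "occurred following the administration of the study drug through the end of the study period". The study period itself is not defined.
- **AE evaluation window (the next sentence):** "Safety will be evaluated during the first 7 days of life or until hospital discharge (whichever comes first".
- **Expected stay (section 3, Safety):** "If the baby remains in the NICU for 2 weeks (uncommon".
- **Long Term Safety (section 3):** a call at 4 months asking about hospitalisations, seizures and other problems, and a request to the primary care provider for the child's "medical records and most recent hematocrit/hemoglobin to assess for safety". The schedule of evaluations repeats the survey at 8-12 months.
- **Reporting route (section 6, monitoring plan, item 4):** "All SAEs will be reported to" the sponsor-investigator "within 24 hours of the site learning of the event". No start or end date is attached. Item 1 has the DSMB review safety every 6 months until the study is complete.
- **Treatment (section 7):** one administration, after which the intervention is over.

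**The concern.** With one dose, the 30 days run from that dose. The discharge clause shortens this for every infant who goes home sooner, which the protocol expects to be most of them. Section 8 names stroke, venous thrombus and death among the known risks of the drug in adults. These are the events for which a gap between discharge and day 30 matters most.

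The rest of the safety plan looks well past discharge. Lasting disability is an SAE criterion, yet development is formally assessed only at 8-12 months. The plan for pure red cell aplasia relies on blood counts ordered in primary care during the first year. Two later contacts ask about hospitalisations. No sentence says whether a serious event found by any of these means is classified and reported as an SAE.

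The stake is what reaches the sponsor-investigator and the DSMB. Seven centres are listed, and each would have to decide for itself how to treat such an event.

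**Working it through.** The plan states no figure on this point, so the check compares the provisions and follows one infant through them.

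**1. Which limit binds.** The dose is given before 24 hours of age (section 3), so 30 days after the dose falls at no more than about 31 days of age. A NICU stay of two weeks is called uncommon. If NICU discharge is close to hospital discharge, discharge is the binding limit for most infants. That is an assumption, because an infant can leave the NICU and stay in hospital.

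**2. The windows compared.**

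| Provision | Ends at |
|---|---|
| AE definition | End of the study period (undefined) |
| AE evaluation | Day 7 of life or discharge, the earlier |
| SAE reporting | 30 days after the dose or discharge, the earlier |
| Safety contacts | 4 months, then 8-12 months |
| DSMB review | Study completion |
| Section 6 SAE route | No period stated |

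The sharpest mismatch lies within the Safety text. An AE is defined study-long, but evaluation stops by day 7 of life. For an infant still in hospital after day 7, AE evaluation has ended while SAE reporting continues.

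**3. One infant.** Take the dose as day 0 and suppose a stroke, thrombosis or death on day 10. Length of stay is not given, so discharge day is assumed:
- discharge on day 4 or day 7: the event meets the AE and SAE definitions but falls after SAE reporting has closed;
- discharge on day 14: the event falls inside the reporting period.

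The same event on the same day is reportable or not according to when the infant went home.

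**4. Readmission.** The hospitalisation criterion covers only prolonging an inpatient stay. A new admission after discharge does not meet it, although both later contacts ask about hospitalisations.

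**5. How late the event could be learned.** Suppose nobody reports it before the 4-month call.
- 4 months = 4 x 365.25 / 12 = 121.75 days; 121.75 - 10 = 111.75, about 112 days.
- The schedule of evaluations uses corrected age, whereas the text of section 3 says 4 months of age. For birth at 34 weeks, with term taken as 40 weeks, add (40 - 34) x 7 = 42 days: 163.75 - 10 = 153.75, about 154 days. This is the longest case, at the lowest eligible gestational age.

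The primary care request has no stated date and could shorten either delay.

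**The case against.** The best defence is that an inpatient-only SAE period is deliberate. The sentence that sets it is the only one in the protocol that gives an SAE reporting period. It fits a definition built around inpatient stay, and post-discharge safety has its own channel in the call, the survey, the primary care records and the DSMB. Unanticipated problems also go to the IRBs under section 4, and section 6 provides for IND safety reports.

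Much of this stands, and it rules out several stronger readings that a reader might infer:

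- **That section 6 contradicts the SAE period.** It does not. Item 4 says who is told and how fast, and can be read as operating within the section 3 period.
- **That there is no safety follow-up after discharge.** There is. What is missing is the link from those contacts to SAE classification and reporting.
- **That a calculable share of promised follow-up is lost.** In the sentence as written, 30 days is an outer cap, not a promised period, so a percentage of it would measure a preference for a fixed window.
- **That the arms will have windows of different length.** Nothing in the documents suggests that one blinded dose changes length of stay.

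The defence does not answer the remaining point. The DSMB notification and IND report in item 4 follow from the site's SAE report, so they do not replace it. The IRB route may catch some events but does not create an SAE record. If the inpatient-only period is intended, the protocol still does not say what happens to a serious event found later.

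**Conclusion.** The concern holds as a gap in the safety rules. Followed as written, the plan does not require SAE reporting of a death, stroke or thrombosis after discharge but within 30 days of dosing. It also does not say how a serious event learned at a later contact is to be classified or reported. The AE definition and the AE evaluation window are not reconciled either. It is not a contradiction between sections 3 and 6, and the documents do not support a claim of bias between arms.

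The number of events affected cannot be estimated, because neither length of stay nor event rates are given. If serious events cluster soon after the dose, few are missed. That discharge is usually the limit rests on the protocol's own remark about NICU stay and on NICU and hospital discharge being close together. The 112 to 154 days assume a day-10 event that no one reports before the call.

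The primary outcome is unaffected. The change should be made because it improves safety capture at little cost, in a trial whose data are meant to support a larger one.

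**What to change.** 1. In the serious adverse events text of section 3, delete the hospital-discharge limit, so that every infant has the protocol's own 30-day post-dose SAE window.
2. Define the study period, and reconcile the 7-day or discharge evaluation window with the AE definition.
3. Add new hospitalisation to the SAE definition. The planned contacts already ask about it.
4. State that any qualifying event learned at the 4-month call, at the 8-12 month visit or from primary care records follows the section 6, item 4 route, with the clock starting when the site becomes aware.
5. Tabulate in-hospital and post-discharge SAEs separately by arm. A common window does not give common ascertainment: the first period is observed directly and the second is not.

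The cost is protocol wording and modest extra reporting work, with no new visit and no change to treatment. The limitation is that post-discharge events will rest on parent recall and primary care records and may be learned late.
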